6.5. Missing Data

All attempts will be made to collect all data per protocol. Any data point that appears to be erroneous or inexplicable based on clinical judgment will be investigated as a possible outlier. If data points are identified as outliers, sensitivity analyses may be performed to examine the impact of including or excluding the outliers. Any substantive differences in these analyses will be reported.

For time to event outcomes, subjects who are lost to follow-up or terminate the study prior to Day 29 and prior to observing/experiencing the event will be censored at the time of their last observed assessment. Other rules for censoring are listed for the specific endpoint in Section 3.3.

For the analysis of the key secondary outcome, subjects who are discharged but are subsequently re-admitted prior to Day 15 without a reported clinical ordinal score, their clinical ordinal score will be imputed at 7, which is the highest value for a hospitalized subject.

For the analyses of the secondary outcomes that involve clinical score (i.e. the key secondary outcome and time to improvement), if a subject is discharged from the hospital (but not to hospice or other end-of-life care) without a previously or concurrently reported clinical score of 1 or 2, then their clinical score at the time of discharge will be imputed as 2, which is the highest value for a non-hospitalized subject. If a subject terminates early from the study while they are hospitalized or completes the study while still hospitalized, the last observed clinical score assessment will be used as their final assessment.

For the modified version of the ordinal score described in Section 4.3, if a subject is discharged from the hospital without a previously or concurrently reported clinical score of 2 or 3, then their clinical score at the time of discharge will be imputed as 3, which is the highest value for a non-hospitalized subject.

For the analyses of the secondary outcomes described in Section 3.3, the following imputation rules will be used for subjects who are lost to follow-up, terminate early from the study, or do not have further outcome data available after discharge for any reason:

- Days of Non-Invasive Ventilation/High-Flow Oxygen:
 - If the subject's clinical status scale is 6 at the last observed assessment, then the subject will be considered to be on non-invasive ventilation/high-flow oxygen through Day 29. The endpoint will be total days when assessments are available plus all imputed days following the last observed assessment.
 - If the subject is not on non-invasive ventilation/high-flow oxygen at the last observed assessment, then the subject will be considered to not be on non- invasive ventilation/high-flow oxygen for the remainder of follow-up. Thus, no additional imputed days will be added to the number of days recorded on available assessments.
- Days of Ventilation/ECMO:
 - If the subject's clinical status scale is 7 at the last observed assessment, then the subject will be considered to be on ventilation/ECMO through Day 29. The endpoint will be total days when assessments are available plus all imputed days following the last observed assessment.
 - If the subject is not on ventilation/ECMO at the last observed assessment, then the subject will be considered to not be on ventilation/ECMO through Day 29. Thus, no additional imputed days will be added to the number of days recorded on available assessments.
- Days of Oxygen:
 - If the subject's clinical status score is 5, 6, or 7 at the last observed assessment, then the subject will be considered to be on oxygen through Day 29. The endpoint will be total days when assessments are available plus all imputed days following the last observed assessment.
 - If the subject is not on oxygen at the last observed assessment, then the subject will be considered to not be on oxygen through Day 29. Thus, no additional imputed days will be added to the number of days recorded on available assessments.
- Days of Hospitalization

- If the subject is discharged and no further hospitalization data are available, then the subject will be assumed to not have been readmitted. Thus, no additional imputed days will be added to the number of days recorded on available assessments. If a subject dies while hospitalized, the number of days of hospitalization will be imputed as 28 days.
- Lab Efficacy (d-dimer and CRP)
 - If results are not available for any visit day(s) but are available for visits before or after that visit, the average of the two nearest visits will be imputed for all missing visits between them. If a subject dies or is otherwise lost to follow-up, their last available observation will be carried forward. If baseline is missing, another pre-treatment dose will be used, or the earliest post-treatment dose will be used.

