3.2. Endpoints

The 8-point ordinal scale is utilized as the principal clinical assessment tool during the study and is the basis for the primary and multiple secondary endpoints. The 8-point ordinal scale is defined as (worst to best):

Category 8: Death;

Category 7: Hospitalized, on invasive mechanical ventilation or ECMO;

Category 6: Hospitalized, on non-invasive ventilation or high flow oxygen devices;

Category 5: Hospitalized, requiring supplemental oxygen;

Category 4: Hospitalized, not requiring supplemental oxygen - requiring ongoing medical care (COVID-19 related or otherwise);

Category 3: Hospitalized, not requiring supplemental oxygen - no longer requiring ongoing medical care. This would include those kept in hospital for quarantine/infection control, awaiting bed in rehabilitation facility or homecare, etc.;

Category 2: Not hospitalized, but has new or increased limitation on activities and/or new or increased requirement for home oxygen over baseline, pre-COVID-19 status;

Category 1: Not hospitalized, patient is back to their baseline, pre-COVID-19 status, that is, no new or increased limitations on activities and no new or increased oxygen use compared with baseline.

Primary Endpoint

Mechanical ventilation free survival by Day 29 will be assessed as the proportion of subjects not meeting criteria for either of the following categories on the 8-point ordinal scale at any time before or at Day 29.:

Category 8: Death

Category 7: Hospitalized, on invasive mechanical ventilation or ECMO

Secondary Endpoints

The key secondary endpoint is the proportion of subjects meeting criteria for each of the 8-point ordinal scale categories on Day 15.

Other Secondary Endpoints are:

- Proportion of subjects not meeting criteria for one of the following ordinal scale categories at any time by Day 29

Category 8: Death

Category 7: Hospitalized, on invasive mechanical ventilation or ECMO

Category 6: Hospitalized, on non-invasive ventilation or high flow oxygen devices

- Days from randomization and cause of death (if applicable).

- The time to recovery defined as the days from randomization to the first day on which the subject satisfies the criteria for any of the following three categories on the 8-point ordinal scale at any time before or at Day 29:

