3.3.7. Recovery and Time to Recovery

A Secondary Endpoint measure requires the time to recovery assessed through Study Visit Day 29. Recovery will be defined as having a value of 1, 2, or 3 on the 8-point ordinal Clinical Status score. The time to recovery will be defined as the elapsed time (in days) from randomization to the earliest day at which a subject reaches recovery. Note that since clinical status assessments are recorded as defined in Section 4.3, the day that is being assessed (not necessarily the day the response is collected) will be used to determine the timing of events. For example, a subject with a score of 5 recorded on study days 1-3 and a score of 3 recorded on study day 4 will have a time to recovery equal to 3 days. It is also possible that a subject has a clinical status ordinal score > 3 reported for a particular day but was subsequently discharged on the same day. If a subject is discharged to a location other than hospice or another hospital the subject will be considered recovered at the time of discharge but may be reviewed by the Endpoint Review Committee, if other data suggests the subject may not be recovered (e.g., the subject is re-admitted). If a subject is discharged to hospice or another hospital, re-admitted, or is a special case where recovery handling may be unclear, the subject's data will be reviewed by the Endpoint Review Committee to make the determination of whether the subject should be considered recovered and, if so, at what time point in the analyses. Subject data to be reviewed as part of this determination will include the reported clinical status scores while hospitalized, where the subject was discharged to (e.g. private residence, rehabilitation facility, long-term care/nursing home, comfort and care), and any information regarding readmittance. Additional information may be solicited to assess recovery.

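### The Section 6.5 discharge imputation does not except transfer to another hospital, and no precedence is stated over the rules that would score such a subject differently

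*SAP*

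**What the plan says.** SAP Section 6.5 sets a discharge rule for "the secondary outcomes that involve clinical score (i.e. the key secondary outcome and time to improvement"). It applies "if a subject is discharged from the hospital (but not to hospice or other end-of-life care) without a previously or concurrently reported clinical score" (the scores meant are 1 and 2), and it assigns a value: "then their clinical score at the time of discharge will be imputed as 2, which is the highest value for a non-hospitalized subject". Section 3.2 defines that value as "Category 2: Not hospitalized, but has new or increased limitation on activities" or a new or increased home oxygen requirement.

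The same section has two other rules that could reach a transferred subject. For the key secondary outcome, a subject discharged and re-admitted before Day 15 without a score is imputed 7. A subject who terminates early while hospitalized, or completes the study still hospitalized, keeps the last observed score.

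For the modified scale, the discharge rule applies "if a subject is discharged from the hospital without a previously or concurrently reported clinical score of 2 or 3" and assigns 3. It has no exception for hospice.

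For time to recovery, Section 3.3.7 handles discharge more carefully: "If a subject is discharged to a location other than hospice or another hospital the subject will be considered recovered". It continues "If a subject is discharged to hospice or another hospital, re-admitted, or is a special case where recovery handling may be unclear", and such cases go to the Endpoint Review Committee. Section 3.3.3 (primary endpoint) describes transfer to another hospital or hospice as a gap in scores while hospitalized, which the blinded committee may review.

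**The concern.** The SAP treats a move to another hospital as a kind of discharge in Section 3.3.7 and does not accept it as recovery without review. Section 6.5 carries over only the hospice half of that safeguard. A subject who is still an inpatient elsewhere can therefore be coded as not hospitalized, for two endpoints that are meant to measure clinical status.

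Two things are at stake. Time to improvement can gain events that did not happen, or happened later. The Day 15 ordinal score is second in the fixed sequence of Section 6.8, so its coding decides whether three further hypotheses are tested. An endpoint in that position should not leave the programmer to choose between 2, 7 and the last observed score.

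**Working it through.** **Rules side by side, for a subject transferred to another hospital with no score of 1 or 2.**

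| Endpoint | Rule that could apply | Result |
|---|---|---|
| Time to recovery (3.3.7) | Committee review | Not automatically recovered |
| Mechanical ventilation-free survival (3.3.3) | Gap while hospitalized, may be reviewed | Committee may decide |
| Time to improvement (3.3.8, defers to 6.5) | Discharge rule | 2 on the transfer day |
| Day 15 score, no visit score (3.3.4, defers to 6.5) | Discharge rule | 2 |
| Same | Re-admission rule | 7 |
| Same | Still hospitalized | Last observed score |

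**Time to improvement.** The two enrolled strata have baseline score 5 or 6. With an imputed score of 2 the gain is 5 − 2 = 3 or 6 − 2 = 4 categories. Both exceed 2, so the one-category and the two-category events both occur on the transfer day, whatever the last observed score was. Section 3.3.8 names no committee review, and the re-admission rule is confined to the key secondary outcome. Because the endpoint is the earliest day of improvement, a worse score obtained later does not undo the event.

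**Modified scale.** A hospice discharge with no earlier score of 2 or 3 is imputed 3, which Section 4.3 defines as not hospitalized with limitations or home oxygen. The main-scale sentence excepts the same subject.

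**DOOR.** Section 3.3.9 also allows imputation under Section 6.5, and scores 1 to 3 form the best DOOR level, recovered. A transfer that Section 3.3.7 does not accept as recovery could be given that level.

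**Size for the Day 15 odds ratio.** The SAP states no figure to reproduce and no transfer rate, so this is an illustration under assumptions. The assumed control distribution for scores 1 to 8 is 25, 45, 1, 5, 8, 4, 7 and 5%. The baricitinib distribution is obtained by multiplying each cumulative odds of a better score by the true odds ratio. A percentage of each arm, truly in Category 6 or 7 and without a Day 15 score, is recoded to 2. A proportional-odds model is then fitted to the expected proportions. An odds ratio above 1 favours baricitinib.

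| Transferred, dexamethasone / baricitinib | True OR 1.0 | True OR 1.3 |
|---|---|---|
| 0% / 0% | 1.00 | 1.30 |
| 1% / 1% | 1.00 | 1.305 |
| 5% / 5% | 1.00 | 1.33 |
| 2% / 1% | 0.97 | 1.27 |
| 4% / 2% | 0.94 | 1.24 |
| 1% / 2% | 1.03 | 1.345 |
| 2% / 4% | 1.06 | 1.39 |

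If instead the same fraction of each arm's Category 6 and 7 subjects is transferred (5% to 25%), a true odds ratio of 1.00 stays at 1.00, and 1.30 becomes 1.299 to 1.294.

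**Size for time to improvement.** Each 1% of about 1500 subjects transferred is 0.01 × 1500 = 15 subjects. That is an upper limit on false events, since a subject who later improves has the event too early rather than wrongly.

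**The case against.** The best case against is that Section 6.5 is aimed at people who have left hospital. It justifies the imputed 2 as a value for a non-hospitalized subject, and Section 3.3.3 describes a transfer as occurring while hospitalized. On that reading a transfer is not a discharge, and the sentence on subjects who terminate or complete while hospitalized already keeps the last observed score. For the Day 15 score, the re-admission rule might give 7. Imputation is permitted rather than required, and an observed Study Visit Day 15 score is used where one exists. Section 4.1 lets discharged subjects have that visit by phone.

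Much of this stands. A reader might infer that every transferred subject will be scored 2 and that deterioration is therefore counted as improvement. The documents do not support that. The Day 15 score of 2 is one of three possible outcomes, and the SAP gives no reasons for transfer, which may also be a stable move. A reader might also infer that one arm is favoured. In a double-blind trial with no treatment effect, nothing in the SAP would make transfers more common in one arm. Time to improvement is outside the testing hierarchy, and the modified scale serves sensitivity analyses only.

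The objection does not remove the defect. Section 3.3.7 does call the move a discharge, so both readings have support in the SAP, and Section 6.5 does not choose between them.

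**Conclusion.** The point holds as a gap and a conflict between rules. For time to improvement, the literal rule creates a one- and two-category event on the transfer day for a subject still in hospital, and Section 3.3.8 has nothing to override it. For the Day 15 score, the defect is missing precedence among three rules, and it matters only where no Study Visit Day 15 score is obtained. For the modified scale, the missing hospice exception is plain.

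The effect is probably small. Under the assumed distribution, balanced transfers leave a null odds ratio at 1.00, and transfer differences of 1 to 2 percentage points between arms shift it by about 3% to 6% toward the arm with more transfers. These figures depend on the assumed Day 15 distribution, on all transferred subjects being in Category 6 or 7, and on their having no Day 15 score. The actual size cannot be derived from the SAP. The reason to act is that the rule feeds a hierarchical endpoint and costs little to settle.

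**What to change.** In Section 6.5:

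- Extend the exception in both the main-scale and the modified-scale sentence to hospice, other end-of-life care, or another hospital.
- For these subjects, where no later score is available, use the last observed inpatient score or the blinded Endpoint Review Committee decision, with 7 as a sensitivity analysis for the Day 15 score.
- State that this rule prevails over the discharge and re-admission imputations.

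In Section 3.3.8, state that transfer to another hospital is not in itself an improvement event. In Section 3.3.9, state that DOOR follows the same rule.

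The cost is a clause in each of two sentences, a precedence statement and two cross-references. Section 3.3.7 already lists discharge destination among the data the committee reviews, so no new data should be needed. The change should be made before the Day 29 database lock, because Section 4.2.6 unblinds the sponsor's division and the coordinating centre after it.

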Category 3: Hospitalized, not requiring supplemental oxygen - no longer requiring ongoing medical care. This would include those kept in hospital for quarantine/infection control, awaiting bed in rehabilitation facility or homecare, etc.;

Category 2: Not hospitalized, but has new or increased limitation on activities and/or new or increased requirement for home oxygen over baseline, pre-COVID-19 status;

Category 1: Not hospitalized, patient is back to their baseline, pre-COVID-19 status, that is, no new or increased limitations on activities and no new or increased oxygen use compared with baseline.

- The time improvement of one category in score defined as the days from randomization to the first day on which the subject satisfies the criteria for a category at least one-step better (e.g., 5 to 4) than their baseline category.
- The time improvement of two categories in score defined as the days from randomization to the first day on which the subject satisfies the criteria for a category at least two-steps better (e.g., 5 to 3) than their baseline category.
- The proportion of subjects meeting the criteria for each of the 8-point ordinal scale categories while hospitalized (Days 3, 5, 8, 11) and on Days 15, 22 and 29.

- Proportion of subjects in each level of the Desirability of Outcome Ranking (DOOR) categories at Day 15 and Day 29. DOOR levels are based on the 8-point ordinal score and the occurrence or absence of SAEs prior to or on the date of the assessment, defined as (best to worst):
 - 1 - Recovered (Category 1, 2 or 3 Ordinal Score)
 - 2 - Improved (≥ 1 category improvement in Ordinal Score compared with baseline) & no SAE
 - 3 - Improved (≥ 1 category improvement in Ordinal Score compared with baseline) & SAE (related or unrelated)
 - 4 - No change in Ordinal Score from baseline & no SAE
 - 5 - No change in Ordinal Score from baseline & SAE (related or unrelated)
 - 6 - Worsening (≥ 1 category worse in Ordinal Score compared with baseline)
 - 7 - Death
- Days of supplemental oxygen (if applicable) up to Day 29.
- Days of non-invasive ventilation/high-flow oxygen (if applicable) up to Day 29.
- Days of invasive mechanical ventilation/ECMO (if applicable) up to Day 29.
- Days of hospitalization up to Day 29.
- D-dimer and CRP on Day 1, while hospitalized (Days 3, 5, 8, 11), and on Days 15 and 29 (if attends in-person visit or still hospitalized).

Safety Endpoints

Safety endpoints are:

- SAEs

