3.3. Study Definitions and Derived Variables

3.3.1. Baseline Value

For efficacy assessments, the baseline value will be defined as the last value obtained prior to randomization. For safety assessments, the baseline value will be defined as the last value obtained prior to the first on-trial dose of any study product (baricitinib, dexamethasone, remdesivir, or placebo). If the exact time of the assessment or the first dose is not available, but collected on the same date, the assessment will be assumed to have occurred prior to receipt of study product.

A small subset of subjects may receive dexamethasone as standard of care on the same day as but prior to randomization then forgo the dexamethasone / placebo component of the Day 1 study product administration. For these subjects, the baseline value of efficacy assessments will be the last value prior to randomization, as in the preceding paragraph. But, for these subjects, the value of baseline safety assessments will be defined as the last value obtained prior to the dexamethasone dose. If the exact time of the assessment of the pre-randomization dexamethasone or on-trial doses of study product are not available, but collected on the same date, the assessments will be assumed to have occurred prior to receipt of study product and prior to randomization.

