For the analysis of mechanical ventilation free survival, subjects will be censored at the time of medication/therapy initiation. For the analysis of the key secondary outcome, if a subject reports use of any of the medications/therapies prior to their Day 15 assessment, then the subject's last clinical status score prior to medication/therapy use will be used as their Day 15 outcome. For the mortality analyses, subjects will be censored at the time of medication/therapy initiation. For the analysis of the proportion of subjects that do not progress to Clinical Status Ordinal Score of 6, 7, or 8 by Day 29, subjects will be censored at the time of medication / therapy initiation. For the recovery analyses, subjects will be censored at the time of medication/therapy initiation. If a subject recovered prior to use of any of the medications/therapies, then the subject will still be counted as a recovery in the sensitivity analysis.

The effect of on-study treatment on select efficacy outcomes will also be explored among subjects who reported use of HMG-CoA reductase inhibitors (statins), angiotensin receptor blockers (ARBs), or angiotensin converting enzyme inhibitors (ACEIs) via subgroup analyses.

Lastly, the effect of treatment on the primary and key secondary efficacy outcomes will be explored via regression modeling controlling for age, duration of symptoms prior to randomization, baseline d-dimer, and baseline CRP values as continuous covariates.

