		PBO + Dexamethasone + RDV	x	xx.x	xx.x, xx.x	xx.x	xx.x, xx.x	x	xx.x	xx.x, xx.x	xx.x	xx.x, xx.x
	Day 29	Baricitinib + PBO + RDV	x	xx.x	xx.x, xx.x	xx.x	xx.x, xx.x	x	xx.x	xx.x, xx.x	xx.x	xx.x, xx.x
		PBO + Dexamethasone + RDV	x	xx.x	xx.x, xx.x	xx.x	xx.x, xx.x	x	xx.x	xx.x, xx.x	xx.x	xx.x, xx.x

N = Number of subjects in the As Treated Population with laboratory data available for the parameter at the specified study visit.
High-sensitivity CRP values are excluded from the summaries.

Programming notes:

Use imputed results for missing data, see Section [6.5](#).

Table 52: Day 60 Ordinal Scores by Treatment Group and Actual Baseline Ordinal Score – mITT Population

Subject Ordinal Score	Baricitinib + PBO + RDV (N=X)						PBO + Dexamethasone + RDV (N=X)						All Subjects (N=X)			
	Baseline Ordinal Score 5 (N=X)		Baseline Ordinal Score 6 (N=X)		All Subjects ^a (N = X)		Baseline Ordinal Score 5 (N=X)		Baseline Ordinal Score 6 (N=X)		All Subjects ^a (N = X)		Baseline Ordinal Score 5 (N=X)		Baseline Ordinal Score 6 (N=X)	
	n	%	n	%	n	%	n	%	n	%	n	%	n	%	n	%
Death at or before Study Visit (8)	x	xx														
Hospitalized, on invasive mechanical ventilation or ECMO (7)	x	xx														
Hospitalized, on non-invasive ventilation or high flow oxygen devices (6)	x	xx														
Hospitalized, requiring supplemental oxygen (5)	x	xx														
Hospitalized, not requiring supplemental oxygen - requiring ongoing medical care (COVID-19 related or otherwise) (4)	x	xx														
Hospitalized, not requiring supplemental oxygen - no longer requires ongoing medical care (3)	x	xx														
Not hospitalized, but new or increased limitation on activities and/or requiring new or increased home oxygen (2)	x	xx														
Not hospitalized, no limitations on activities (1)	x	xx														

N = Number of subjects in the mITT Population with a Day 60 ordinal score.
n = Number of subjects with the reported ordinal score at Day 60.
^a[X] additional subjects are included in the 'All Subjects' column that were enrolled with a baseline ordinal score of 4. [Include as applicable]

Table 53: Day 60 Change in Ordinal Score from Day 29 by Treatment Group and Actual Baseline Ordinal Score – mITT Population

Status at Day 29	Ordinal Score Change at Day 60	Baricitinib + PBO + RDV (N=X)						PBO + Dexamethasone + RDV (N=X)						All Subjects (N=X)					

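### Section 6.5 lets a post-treatment d-dimer or CRP value stand in as baseline and fills unmeasured visits, even after death, so the Table 51 means can be biased and its N misstated

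*SAP*

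**What the plan says.** Section 6.5 (Missing Data, Lab Efficacy) sets three rules for d-dimer and CRP.

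- **Missing baseline:** "If baseline is missing, another pre-treatment dose will be used, or the earliest post-treatment dose will be used". 'Dose' must mean a laboratory value here. Another pre-treatment value is tried first, and the post-treatment value is the fallback.
- **Gaps between visits:** "the average of the two nearest visits will be imputed for all missing visits between them".
- **After death or loss:** "If a subject dies or is otherwise lost to follow-up, their last available observation will be carried forward".

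Section 3.3.1 defines baseline differently: "For efficacy assessments, the baseline value will be defined as the last value obtained prior to randomization". Its safety definition, the last value before the first on-trial dose, also allows nothing post-treatment.

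Section 3.2 plans these samples on Day 1, "while hospitalized (Days 3, 5, 8, 11), and on Days 15 and 29 (if attends in-person visit or still hospitalized"). Section 4.1 allows the Day 15 and Day 29 visits by phone, with clinical data only.

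Table 51 (Appendix 1) gives means with 95% intervals, absolute and as change from baseline, by arm and visit. Its programming note reads "Use imputed results for missing data, see Section" 6.5. Its title names the mITT population, but its footnote reads "N = Number of subjects in the As Treated Population with laboratory data available for the parameter at the specified study visit". Table 90, the companion laboratory table, leaves out both markers.

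Section 6.4 also plans regression models for the primary and key secondary outcomes with "baseline d-dimer, and baseline CRP values as continuous covariates".

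**The concern.** Section 2 describes both study drugs as anti-inflammatory strategies, so the early movement of an inflammation marker is what this secondary endpoint is meant to show. A baseline drawn after dosing has begun removes that early movement for the subjects concerned.

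The filling rules raise a second problem. Missing samples are built into the schedule, because in-hospital sampling ends at discharge and the later visits need attendance in person. Carrying the last value forward, or averaging across a gap, holds the marker near an earlier level while it may still be changing. After death there is no value to estimate. Table 51 then presents measured and filled values together under an N described as subjects with data available, so a reader cannot tell how much was measured.

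**Working it through.** The SAP gives no missing rate, standard deviation or expected change for these markers, so it has no figure to reproduce. The check has an algebraic part, which needs only the rule, and a simulation on assumed inputs.

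**1. Post-treatment baseline.** Let μ₃ and μₜ be the true mean changes at Day 3 and at a later visit t. Let a share m of subjects have no pre-treatment value and take Day 3 as baseline. Assume that a missing baseline is unrelated to the size of the change.

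- Day 3: those subjects contribute exactly 0, so the mean becomes (1−m)·μ₃ + m·0 = (1−m)·μ₃.
- Later visit: they contribute a mean of μₜ−μ₃, so the overall mean becomes (1−m)·μₜ + m·(μₜ−μ₃) = μₜ − m·μ₃.

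For m = 2%, 5%, 10% and 20% (assumed), the Day 3 mean change is 0.98, 0.95, 0.90 and 0.80 of its true size. At every later visit the shortfall is the fixed amount m·μ₃.

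**2. All three rules together.** One arm of 500 was simulated with a falling log-normal CRP, 150 runs per scenario. None of these inputs comes from the SAP:

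- autocorrelation between visits of 0.7 or 0.4;
- 5% or 10% missing baseline;
- 6% or 0% deaths;
- severity-dependent discharge;
- 50% attendance in person at Days 15 and 29 after discharge.

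Last values were carried forward to all later missing visits. Section 6.5 states this for death and loss to follow-up. It does not clearly say what happens to a subject followed by phone with no later sample, so applying it there is an assumption.

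| Missing baseline / correlation / deaths | Day 3 true → filled | Day 15 true → filled | Day 29 true → filled | Measured Day 29 pairs |
|---|---|---|---|---|
| 5% / 0.7 / 6% | −24.9 → −23.7 | −107.5 → −88.8 | −129.3 → −101.5 | 224 of 500 |
| 10% / 0.7 / 6% | −24.9 → −22.4 | −107.1 → −87.3 | −129.2 → −100.2 | 213 of 500 |
| 5% / 0.4 / 6% | −24.9 → −23.6 | −108.0 → −88.4 | −129.9 → −101.5 | 223 of 500 |
| 5% / 0.7 / 0% | −24.2 → −23.2 | −107.1 → −92.2 | −129.1 → −106.1 | 237 of 500 |

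Day 3 follows the algebra: 23.7/24.9 = 0.95 and 22.4/24.9 = 0.90. The last row is the cleanest, since no value after death enters the true mean. Its Day 29 shortfall is 129.1 − 106.1 = 23.0. The baseline rule accounts for about 0.05 × 24.2 = 1.2 of that, and carry-forward for nearly all the rest. With 6% deaths the shortfall is 27.8 to 29.0.

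**3. Standard error.** At Day 29 the calculated standard error of the filled mean was 7.55, 7.29, 7.91 and 7.37. The spread of that mean over the runs was 7.42, 6.65, 7.66 and 7.92, a ratio of 0.93 to 1.10. The formula therefore describes the mean of the filled values about correctly. The interval contained the true mean in only 3% to 13% of runs because it was centred in the wrong place.

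**4. Observed values alone.** Raw observed means are not a full remedy. With correlation 0.7 and 5% missing baseline, the Day 11 observed mean was −131.6 (6% deaths) or −127.6 (no deaths), against true values of −89.0 and −88.4. Those still in hospital are a selected group.

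**The case against.** The strongest objection is about consequence. Table 51 is descriptive by arm, with no between-arm difference and no p-value. D-dimer and CRP lie outside the fixed sequence in Section 6.8. The post-treatment value is a last resort, Day 1 samples are planned for everyone, and the SAP gives no rate at which the fallback would apply. Measured values could be recovered from Listing 23. Figure 34 may show medians for these markers, though it does not say whether filled values are used. All of this stands and limits the weight of the point.

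Three stronger readings are not supported.

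- **Interval width.** A reader might infer that with a fraction f of values real, coverage is 2Φ(1.96√f) − 1, or about 83% at f = 0.5 and 78% at f = 0.4. That treats filled values as duplicated information. Here each comes from the subject's own data and is independent across subjects. With no time trend, 500 subjects, 50% or 40% real values and correlations of 0.2, 0.5 and 0.8, simulated coverage was about 95% in all six cases. The harm is bias and a misdescribed N.
- **Adjusted models.** A reader might infer that the filled baseline enters the primary and key secondary models. The rule sits in a list for secondary outcomes, and only Table 51 is told to use it. The SAP is silent on the models.
- **Timing.** A reader might infer that most subjects have left hospital by Day 5. The ACTT-2 median recovery of 7 days quoted in Section 2 does not support that, and recovery includes Category 3, which is still in hospital.

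**Conclusion.** The point holds as a defect of wording and analysis in Section 6.5 and Table 51, and it should be corrected. The conflict with Section 3.3.1 is plain on the text. Followed as written, the fallback shrinks the Day 3 mean change by exactly the share of baselines it fills, provided that missingness is unrelated to the change.

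Carry-forward and averaging bias the means whenever the markers change over time. In the assumed scenarios the Day 29 mean change came out 18% to 22% too small (23.0/129.1 to 29.0/129.2). Those percentages illustrate direction under a falling marker and heavy post-discharge missingness. They are not estimates for this trial. Only single arms were simulated, so no bias in the contrast between arms has been shown. It may partly cancel if missingness is alike in both arms.

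No confirmatory conclusion depends on this. The supportive covariate-adjusted models are touched only if the fallback is applied there.

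**What to change.** - In Section 6.5, delete the post-treatment fallback. Baseline is a pre-treatment value as in Section 3.3.1, and otherwise missing. Correct 'dose' to 'value'.
- Impute no d-dimer or CRP value after death.
- Base Table 51 on observed values, with the true N at each visit and one population named in both title and footnote.
- Replace carry-forward and neighbour averaging with a likelihood-based repeated-measures model or multiple imputation. Either is acceptable. State its missing-at-random assumption, because sampling stops at discharge and observed means alone describe a selected group.
- In Section 6.4, state that no post-treatment value may serve as the baseline d-dimer or CRP covariate, and say how a missing covariate is handled.

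The cost is SAP wording, a revised table shell and one standard analysis, with no new data collection. The change-from-baseline columns will hold slightly fewer subjects, and the intervals will be wider. In the simulation the Day 29 standard error was 10.4 to 11.0 from measured pairs, against 7.3 to 7.9 with filling.
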